4.0 BACKGROUND AND RATIONALE

4.1 Background

4.1.1 Introduction

The growing opioid-use epidemic in the U.S. has been associated with a significant increase in the prevalence of pregnant women with opioid use disorder (OUD)¹⁻⁴ and neonatal abstinence syndrome (NAS)/neonatal opioid withdrawal syndrome (NOWS).^{5, 6} NAS/NOWS is associated with adverse health effects for the infant⁷⁻⁹ and with costly hospitalizations.⁶ In 2012, the average length of stay (LOS) for NAS/NOWS was 16.9 days and the average cost was \$66,700.⁶ In 2013, about 4% of total neonatal intensive care unit days were attributed to infants with NAS/NOWS, compared to just 0.6% in 2004.¹⁰ The American College of Obstetricians and Gynecologists (ACOG) Committee, together with the American Society of Addiction Medicine, published their recommendation in 2012 that opioid-dependent pregnant women should not be tapered off opioids and should be treated with methadone or, possibly, buprenorphine (BUP).¹¹ A more definitive recommendation for either methadone or BUP treatment was made by the World Health Organization in 2014.¹² This opinion has been maintained based on more recent literature reviews,¹³ and the relative advantages/disadvantages of each treatment approach have been further delineated. Relative to methadone, BUP offers the advantages of greater convenience for pregnant women and lower NAS/NOWS severity in their infants.¹⁴ Some disadvantages of BUP include increased risk of diversion,¹⁵ poorer adherence,¹⁵ greater treatment dropout,¹⁶⁻¹⁸ and daily peak-trough effects.¹⁹ While applicable to individuals with OUD in general, these disadvantages may be more pronounced in pregnant women.

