Infant Development. Recent reviews have noted the need to consider the longer-term impact of in utero exposure to opioid maintenance on children, for which there is currently a dearth of research.¹⁴ The 6-month and 12-month versions of the Ages and Stages Questionnaire, third edition (ASQ-3)⁷¹ will be used to screen infants for developmental issues. The ASQ-3 is a validated, parent-administered screen used throughout the world⁷¹⁻⁷³ and deemed appropriate for assessing infants exposed to opioids in utero.¹³ An association between FHRV and development has been found in a number of studies.⁷⁴⁻⁷⁶ Furthermore, a recent study found that the relationship between maternal depression and neonatal neurobehavioral immaturity was mediated by FHRV.⁷⁷ It is thus predicted that fetal behavior, as measured by FHRV, will be a significant predictor of scoring below the ASQ-3 cut-off. Research has also found a relationship between NOWS severity and infant development^{78, 79} and it is, thus, predicted that NOWS-related outcomes will predict ASQ-3 scores.

NOWS-related outcomes. Approximately 50% of infants born to women on opioid maintenance treatment will experience NAS/NOWS.¹⁴ Factors that can impact NOWS include maternal polysubstance use,^{32, 80} EGA at delivery and birth weight,^{81, 82} and nonpharmacological treatment approaches.⁸³ Controlling for these factors as needed, the mechanisms by which BUP-XR, relative to BUP-SL, may impact NOWS-related outcomes will be evaluated. It has been hypothesized that the daily peak-to-trough fluctuation associated with opioid maintenance treatment results in the fetus experiencing withdrawal, which increases the incidence and severity of NAS/NOWS.⁷⁰ Consistent with this hypothesis, a retrospective study evaluating NAS/NOWS incidence in infants born to mothers maintained on a split-dosing schedule of methadone reported a lower incidence of NAS/NOWS (29%)⁷⁰ relative to the 50% typically associated with methadone maintenance.^{14, 83} It is thus predicted that fetal behavior, as measured by FHRV, will be a significant predictor of NOWS outcomes.

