7.1.2 Key Secondary Outcomes (Primary Objective)

7.1.2.1 NOWS Severity

NOWS severity will be assessed by total days of opioid treatment during the hospital stay, which is a definition that has been used in past research.⁶⁰ This outcome will be abstracted from the medical record.

7.1.2.2 *Postpartum Illicit Opioid Abstinence*

Illicit opioid abstinence postpartum will be assessed in a similar fashion to illicit opioid abstinence during pregnancy (see **section 7.1.1**).

7.2 **Secondary Outcome Measures (Primary Objective)**

7.2.1 **Mother Secondary Outcomes**

7.2.1.1 *BUP Medication Adherence*

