10.3 Analysis Plan

Each primary and secondary efficacy outcome measure will be analyzed for the intent-to-treat (ITT) population.

The primary outcome will be assessed at a 2.5% significance level for non-inferiority, as recommended by the FDA.¹⁷⁶ If the test of BUP-XR being non-inferior to BUP-SL is statistically significant, then the superiority of the extended-release formulation over the sublingual formulation will be evaluated. There is no need to adjust for this second test if the initial test of non-inferiority is statistically significant. The infant key secondary outcome will be analyzed at the 5% significance level for superiority, and will be interpreted cautiously given the lack of adjustment for multiple testing and will use confidence intervals where possible. The other key secondary outcome (illicit opioid abstinence during postpartum) will be assessed at a 2.5% significance level for non-inferiority.

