Total days of opioid treatment. Total days of infant opioid treatment will be obtained from the medical record. There are extensive covariates to be included in modelling for the infant outcomes (**Table 2**) at the mother-, infant-, and delivery-hospital-level. Explanation for these covariates is provided in **section 7.4**. Since this outcome measure is a count variable and there are covariates requiring adjustment, modelling will utilize Poisson regression. The treatment effect will be measured by the regression coefficient for treatment assignment in the model ($H_0: \beta=0$; $H_1: \beta \neq 0$).

Illicit opioid abstinence during postpartum. The analytic approach will follow the one outlined above for testing the primary outcome.

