10.3.3 Secondary Outcomes

For binary secondary outcomes, such as the proportion of infants requiring opioid medication, and the proportion with an ICD-10 code indicating NOWS, logistic regression or Pearson's χ^2 test of association or another appropriate method will be used to assess the relationship with treatment assignment. Continuous outcomes, such as medication adherence, opioid craving during pregnancy and infant weight at delivery, will be modelled using ANOVA or an appropriate alternative (e.g., quantile regression) to evaluate the effectiveness of BUP-XR. Lastly, the number of opioid overdoses can be modeled as a count variable with possibly zero-inflation, thus a method such as Poisson or Zero-Inflated Poisson regression can be implemented.

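### Poisson regression for days of infant opioid treatment has no provision for overdispersion, so the key secondary NOWS test would not hold its nominal 5% level

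*Combined protocol and SAP*

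**What the plan says.** Section 7.1.2.1 defines the outcome: "NOWS severity will be assessed by total days of opioid treatment during the hospital stay". An infant given no opioid therefore scores zero. Section 10.3.2 chooses the model: "Since this outcome measure is a count variable and there are covariates requiring adjustment, modelling will utilize Poisson regression". It then defines the test: "The treatment effect will be measured by the regression coefficient for treatment assignment in the model", with a null of β=0 against a two-sided alternative. Section 10.3 sets the level: "The infant key secondary outcome will be analyzed at the 5% significance level for superiority".

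The covariates come from Table 2 (section 7.4.2), which section 7.4.2 introduces as a list of candidates. One of them is pharmacotherapy received by the infant for NAS/NOWS; its coding is not defined.

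No scale parameter, robust variance, alternative count model or fallback is named for this outcome. Other outcomes do have one. Section 10.3.2 offers quantile regression if the mixed model for the primary outcome fails its assumptions. For overdose counts, section 10.3.3 says "a method such as Poisson or Zero-Inflated Poisson regression can be implemented".

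**The concern.** Poisson regression takes the variance to equal the mean. Section 4.4.2 says: "Approximately 50% of infants born to women on opioid maintenance treatment will experience NAS/NOWS". Infants without NOWS should contribute zeros, while those treated can contribute courses of many days. Days within one course are also not independent events. Such a mixture has a variance well above its mean, and default Poisson standard errors are then too small.

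This is the only one of the three key hypotheses framed as superiority. If its p-value and confidence interval are too optimistic, a chance difference between arms, in either direction, could be reported as an effect of the formulation on infants.

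**Working it through.** **The plan's own figures.** No power, mean, variance or dispersion is given for this outcome; its only stated figure is the 5% level. The one computed power, Table 8, is for the primary outcome, and it reproduces. With variance 0.11 and 100 per arm, SE = √(0.11×2/100) = 0.0469 and power = Φ(0.15/0.0469 − 1.96) = Φ(1.24) = 89.2% (Table 8: 89.0%). With 88 per arm, SE = 0.0500 and power = Φ(3.00 − 1.96) = 85.1% (Table 8: 84.9%).

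**Inputs.** From the documents: about 200 participants randomized 1:1, a two-sided 5% test, and NAS/NOWS in about 50% of infants as an upper guide to the share treated. Assumed, because the documents do not give them: the share treated p, and the mean m and SD s of days among treated infants.

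**Formulas, no covariates.** The mean is pm and the variance is p(s²+m²) − (pm)². Let φ = variance/mean. The true standard error is √φ times the model-based one, and the actual two-sided error is 2[1 − Φ(1.96/√φ)].

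Example with p=0.5, m=10, s=7: mean 5; variance 0.5×(49+100) − 25 = 49.5; φ = 9.9; √φ = 3.15; error = 2[1 − Φ(0.62)] = 53%.

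| p | m | s | φ | SE ratio | Actual error |
|---|---|---|---|---|---|
| 0.5 | 5 | 3 | 4.3 | 2.07 | 35% |
| 0.5 | 10 | 4 | 6.6 | 2.57 | 45% |
| 0.5 | 10 | 7 | 9.9 | 3.15 | 53% |
| 0.5 | 15 | 10 | 14.2 | 3.76 | 60% |
| 0.5 | 15 | 15 | 22.5 | 4.74 | 68% |
| 0.3 | 10 | 7 | 11.9 | 3.45 | 57% |

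The zeros alone are enough. With half zeros and exactly Poisson days among the treated, φ = 1 + 0.5m, which gives 29% error at m=5, 42% at m=10 and 50% at m=15.

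**Simulation, no covariates.** Null trials at N=200, 4,000 per setting, reject as follows (share treated, mean/SD):
- 50%, 5/3: 35%
- 50%, 10/7: 53%
- 50%, 15/8: 57%
- 50%, 15/10: 59%
- 30%, 10/5: 52%
- 20%, 6/3: 44%
- essentially all infants treated, 15/8: 33%

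In smaller runs at N=200 and 50% treated, the simulated SE ratio is 2.06 for 5/3 and 3.73 for 15/10. At 50% and 10/7, a moderately prognostic covariate changes little (51%). Giving 3% of infants the worst observed value, as section 10.3.5 does for missing records and non-live births, raises the rate to 60%.

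**Simulation with pharmacotherapy as yes/no.** The untreated zeros are then fitted exactly and only treated infants inform the test, so φ = s²/m:
- 6/3: φ = 1.5, ratio 1.22, about 11%
- 10/5: φ = 2.5, ratio 1.58, about 22%
- 15/8: φ = 4.27, ratio 2.07, about 34%
- 15/10: φ = 6.67, ratio 2.58, about 45%

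Simulated rejection across these settings is about 10% to 46%. Inflation under this coding needs s² > m, for example an SD above √10 = 3.2 days at a mean of 10.

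**With a corrected variance.** On the same null data without covariates, a robust standard error rejects in 4.6% to 5.3% (4,000 trials per setting). In the smaller runs (300 to 600 trials, all covariate codings), robust and quasi-Poisson errors lie between about 2% and 8%, consistent with 5% given simulation error of 2 to 2.5 points.

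**The case against.** The strongest objection concerns size. A reader might infer from the table that Poisson standard errors here are 2.5 to 4 times too small and that about half of null trials would reject. The documents do not support that as a fact. The 50% in section 4.4.2 is the occurrence of NAS/NOWS, not the share given opioids. The 16.9 days in section 4.1.1 is a 2012 average length of stay, not days of treatment, and has no SD. Section 4.3.4 requires delivery hospitals with a written protocol and rooming-in, and associates these with fewer treatment days and less need for drug treatment. The plan also includes covariates, and a yes/no pharmacotherapy term removes the zeros and much of the inflation. All of this stands, and it limits the claim to a range.

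A reader might also infer that the plan prescribes the model-based standard error. It names no variance estimator. Section 10.4.2 mentions a standalone SAP, but only for details of the power simulation. What is supportable is that no correction is specified and that Poisson regression run by default uses the model-based error.

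Two defences do not hold. The caution promised in section 10.3 is tied to multiple testing and relies on confidence intervals, which would be too narrow by the same factor. The sensitivity analyses in section 10.3.5 concern missing data and COVID-19. Nor does yes/no coding rescue the plan: the test stays inflated in the settings tried, and it would be conditioned on a post-randomization component of the outcome itself.

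**Conclusion.** The concern holds as a gap in specification. Followed as written with default Poisson errors, the NOWS test exceeds its stated 5% level in every setting tried. Under assumed day distributions at N=200, the rate is about 35% to 60% without covariates, and wider inputs at 50% treated reach a ratio of about 4.7 and 68%. It is about 10% to 46% if pharmacotherapy enters as yes/no. The direction without that covariate follows from the expected zeros; the magnitude depends on p, m, s and covariate coding, none of which the documents fix. The primary non-inferiority conclusion is not affected.

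**What to change.** In section 10.3.2, keep the log-link model, the rate ratio and the null of β=0. State that the test and confidence interval will use a pre-specified robust (sandwich) or quasi-Poisson variance, one of the two named in advance, and that the model-based Poisson standard error will not be used. Negative binomial or hurdle models and rank or permutation tests are optional and not needed to restore the level; a hurdle model would also replace the single rate ratio with two treatment coefficients. It would help to state in the same edit whether and how the pharmacotherapy covariate enters, since that changes what the treatment coefficient means.

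The cost is a short text change and a wider confidence interval. No additional data are needed.

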10.3.3 Secondary Outcomes

For binary secondary outcomes, such as the proportion of infants requiring opioid medication, and the proportion with an ICD-10 code indicating NOWS, logistic regression or Pearson's χ^2 test of association or another appropriate method will be used to assess the relationship with treatment assignment. Continuous outcomes, such as medication adherence, opioid craving during pregnancy and infant weight at delivery, will be modelled using ANOVA or an appropriate alternative (e.g., quantile regression) to evaluate the effectiveness of BUP-XR. Lastly, the number of opioid overdoses can be modeled as a count variable with possibly zero-inflation, thus a method such as Poisson or Zero-Inflated Poisson regression can be implemented.

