
7.2.1.2 *Drug and Alcohol Abstinence*

Drug and alcohol abstinence during pregnancy and postpartum are secondary outcomes and will be assessed in a fashion similar to the assessment of illicit opioid abstinence, but rather than being restricted to illicit opioid use, will include alcohol and other drugs of abuse. Missing urine samples will be imputed as positive.

7.2.1.3 *The Opioid Craving Scale*

Craving will be assessed with the Opioid Craving Scale, which was utilized in CTN-0030 and shown to have predictive validity.¹¹² The total score is calculated by averaging the scores from three visual analogue scales which assess craving, cue-induced craving, and likelihood of using.

7.2.1.4 *Adequacy of Prenatal Care Utilization*

Kotelchuck's Adequacy of Prenatal Care Utilization (APNCU) index,¹¹³ which is a well-established index,¹¹⁴ will be used to assess the adequacy of prenatal care. The APNCU includes two indices that are combined to obtain a total score. One index is the timing of prenatal care initiation scored in 4 categories [EGA months: 1) 1 and 2; 2) 3 and 4; 3) 5 and 6; and 4) 7 to 9]. The second is the ratio of observed to expected visits based on the length of time between the first prenatal care visit and delivery, scored in 4 categories: 1) Inadequate (received less than 50% of expected visits); 2) Intermediate (50%-79%); 3) Adequate (80%-109%); 4) Adequate Plus (110% or more). The information for the APNCU will be derived from either medical records or the birth certificate. The % of expected visits attended prior to study randomization will be included as a baseline covariate in analyses.

7.2.1.5 *The Short Opiate Withdrawal Scale (SOWS)-Gossop*

The SOWS-Gossop¹¹⁵ will be used to measure opioid withdrawal symptoms. The SOWS-Gossop, which is a self-administered scale that includes 10 items, rated on a scale of 0 (none) to 3 (severe), is a validated instrument with good reliability.¹¹⁶ It will be completed following the schedule in **Table 3**.

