	Pre- Screen	Screen/ Base ¹	Random- ization ²	Week 3	Monthly Post-rand ³		Month 1	Month 2	Month 3	Month 4	Month 5	Month 6	Month 7	Month 8	Month 9	Month 10	Month 11	Month 12	
Research Visits		X	X	X	X		X		X			X			X			X*	
Sample Characteristics																			
Pregnancy Hx, HIV, Hepatitis C		X																	
Trauma History Screen		X																	
Psychosocial status		X																	
Pt. Health Questionnaire-9		X					X											X	
Thoughts about Abstinence		X																	
Timeline Followback (drug/alcohol/tobacco)		X																	
Fagerström		X																	
Opioid Overdose Risk Survey		X																	
Marijuana Use Assessment		X																	
Safety Assessments																			
Hospital Anxiety and Depression Scale		X		X	X		X		X			X			X			X	
Prior/Concomitant Meds		X		X	X		X		X			X			X			X	
Fetal Outcomes ⁴						X													
Maternal Delivery Outcomes ⁴						X													
Birth/Neonatal Outcomes ⁴						X													
Mother Efficacy Assessments																			
Opioid Craving Scale		X		X	X		X		X			X			X			X	
Adequacy of Prenatal Care Utilization ⁴						X													
Opioid Overdose Tracking				X	X		X		X			X			X			X	
SOWS-Gossop		X		X	X		X		X			X			X			X	
Other Assessments																			
PROMIS and NMOS		X			X		X		X			X			X			X	
Treatment Services Review		X			X		X		X			X			X			X	
Maternal Research Visit Compensation		\$120		\$40	\$60		\$60		\$60			\$60			\$60			\$70	
Table 3 continued on next page																			

Table 3 continued on next page

CONFIDENTIAL

Table 3: Overview of Assessments and Procedures																				
Perinatal Phase:	Pregnancy					Delivery & Immediate Post-partum	Post-partum													As Needed
	Pre- Screen	Screen/ Base ¹	Random- ization ²	Week 3	Monthly Post-rand ³		Month 1	Month 2	Month 3	Month 4	Month 5	Month 6	Month 7	Month 8	Month 9	Month 10	Month 11	Month 12		
Research Visits		X	X	X	X		X		X			X			X			X*		
Infant Assessments																				
NOWS-related and discharge outcomes ⁴						X														
ASQ-3 ⁹											X							X		
Family Psychosocial Screen ⁹											X							X		
Medical Record Releases ⁺																			X	
Infant assessment compensation											\$30							\$30		
Administrative Forms																				
Locator information form(s) ⁺	X	X			X		X		X			X			X				X	
Study Eligibility			X																	
Study Completion																		X		
Missed Visit and Visit Documentation Form		X	X	X	X		X	X	X	X	X	X	X	X	X	X	X	X		
End of Medication																			X	

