8.6 Participant Reimbursement

Participants will be reimbursed for their transportation, inconvenience, and time. The form of this reimbursement will be determined by the study sites. As noted in **Table 3**, the number of visits during pregnancy will depend on the EGA at randomization and the timing of delivery. The number of weekly Medication Check Visits that do not coincide with a research visit and, thus, for which participants will be reimbursed to help cover transportation costs, are estimated to range from 7-36 visits. The estimated potential range of research monthly visits is 2-8. The recommended reimbursement schedule for participant visits and completion of infant-related assessments is provided in **Tables 4a** and **4b**, respectively. The reimbursement amounts listed in Table 4a will be reduced by \$10 if the study participant does not travel to attend the visit.

Table 4a: Reimbursement schedule for participant research visits

Visit	Total per Visit (\$)	Total # of Visits	Grand Totals (\$)
Screening/baseline			\$120
Week 3 visit	\$40	1	\$40
Weekly Medication Check visits during pregnancy*	\$20	7 - 36	\$140 - \$720
Monthly Research visits during pregnancy	\$60	2 - 8	\$120 - \$480
Weekly Medication Check visits postpartum*	\$20	48 - 52	\$960 - \$1040
Postpartum Research visits (1, 3, 6, 9 months)	\$60	4	\$240
Postpartum visit month 12	\$70	1	\$70
Total			\$1,690 - \$2,710

*Not coinciding with a research visit

Table 4b: Reimbursement schedule for infant-related assessments

Visit	Total per Visit (\$)	Total # of Assessment Points	Grand Totals (\$)
6-month postpartum assessments	\$30	1	\$30
12-month postpartum assessments	\$30	1	\$30
Total			\$60

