10.1.2 Secondary Hypotheses

It is also hypothesized that the BUP-XR, relative to the BUP-SL, group will have better:

1. Mother outcomes during pregnancy including significantly:
 - greater proportion of BUP adherent days during pregnancy
 - greater proportion of drug-negative urine samples
 - less opioid craving as assessed by the opioid craving scale
 - better prenatal care utilization as assessed with the APNCU index
2. Mother outcomes postpartum including significantly:
 - greater proportion of BUP adherent days
 - greater proportion of drug-negative urine samples
 - fewer opioid overdoses
 - less opioid craving as assessed by the opioid craving scale
3. Infant outcomes including significantly:
 - lower proportion of infants requiring opioid medication
 - shorter infant hospital length of stay
 - lower proportion of infants for whom adjunct medications are used to treat NOWS
 - lower proportion of infants with an ICD-10 code indicative of NOWS
 - larger head circumference
 - greater weight and length
 - greater gestational age at delivery
 - greater proportion of infants scoring above the ASQ-3 cut-off

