10.3.4 Safety Analyses

10.3.4.1 Adverse Events

For mothers, adverse events (AEs), including serious adverse events (SAEs), will be summarized by system organ class and preferred term using MedDRA (The Medical Dictionary for Regulatory Activities). Adverse events will be presented as the number and proportion of participants experiencing at least one incidence of each event and will be presented overall and by treatment

group. Listings of serious adverse events will be provided, sorted by treatment, system organ class, and preferred term. Detail in these listings will include severity, relationship to study drug, and outcome. The number of participants experiencing each type of AE and SAE may be compared between treatment arms using either Fisher's Exact test or Pearson's χ^2 test, as appropriate.

For infants, events will be summarized in a similar way, however, infant death, congenital anomalies in all infants and other infant SAEs in breastfed infants are reportable.

10.3.4.2 *The Hospital Anxiety and Depression Scale (HADS)*

Depression and anxiety scores, as measured by the HADS, will be summarized using descriptive statistics over time by treatment arm. Repeated measures mixed models may be used to compare the treatment groups on the depression and anxiety symptoms from screening/baseline through 12 months postpartum.

10.3.4.3 *Fetus/Delivery-Related Outcomes*

Fetus/delivery-related outcomes will be summarized by treatment arm. Listings may be provided for fetus- or delivery-related outcomes of particular concern and will be broken down by treatment arm.

10.3.4.4 *Birth/Neonatal Outcomes*

Outcomes related to the birth and/or neonate, such as head circumference or the need for resuscitation, will be summarized by treatment arm and listings may be provided for adverse outcomes, as needed.

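### Opioid craving is scored repeatedly in each woman, but section 10.3.3 assigns it to ANOVA or an open alternative without defining the unit of analysis or handling within-woman correlation

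*Combined protocol and SAP*

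**What the plan says.** Section 10.1.2 lists "less opioid craving as assessed by the opioid craving scale" as a directional hypothesis for BUP-XR, once for pregnancy and once for postpartum. Section 7.2.1.3 defines the score at a single administration: "The total score is calculated by averaging the scores from three visual analogue scales". It gives no rule for combining administrations.

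The Mother Efficacy block of Table 3 schedules the "Opioid Craving Scale" at screening/baseline, week 3, each monthly pregnancy visit, and postpartum months 1, 3, 6, 9 and 12. Section 8.6 states: "The estimated potential range of research monthly visits is 2-8".

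Section 10.3.3 groups craving during pregnancy with medication adherence and infant weight: "Continuous outcomes, such as medication adherence, opioid craving during pregnancy and infant weight at delivery, will be modelled using ANOVA". The sentence does not stop at ANOVA. In full, these outcomes "will be modelled using ANOVA or an appropriate alternative (e.g., quantile regression) to evaluate the effectiveness of BUP-XR". Postpartum craving is not named there, but it falls under the same rule for continuous outcomes.

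For the HADS, which has the same Table 3 schedule, section 10.3.4.2 says: "Repeated measures mixed models may be used to compare the treatment groups on the depression and anxiety symptoms". Section 10.10 likewise mentions a mixed model for the repeated Bayley scores.

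Section 10.3 sets significance levels for the primary and key secondary outcomes only. Section 10.3.5 gives imputation rules for the key outcomes only.

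**The concern.** A reader cannot tell from section 10.3.3 what one observation is in the craving analysis. It could be a visit, a woman's average, her last score, or one chosen visit. Nor does the plan say how the baseline score enters or what happens when a woman misses visits or leaves.

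ANOVA and quantile regression in their ordinary form assume independent observations. Scores from one woman are not independent. Elsewhere the plan is explicit. Section 10.3.2 reduces the weekly urine screens to one percentage per woman, and section 7.2.1.1 reduces adherence to one proportion. Craving gets no such reduction.

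The choice matters because less craving is a claimed maternal benefit in both phases, the trial is open-label, and the candidate analyses differ in error rate and precision. With no stated rule, the choice could be made after the data are seen.

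**Working it through.** **Plan's own figures.** The plan gives no error rate, power or correlation for craving, so there is nothing to reproduce on this point. The Table 8 power for the primary outcome does reproduce. With variance 0.11 and margin 0.15, power is Φ(0.15/√(2×0.11/n) − 1.96). At n = 88 per arm this is Φ(3.00 − 1.96) = 85.1% (stated 84.9%). At n = 100 it is Φ(3.20 − 1.96) = 89.2% (stated 89.0%). That analysis uses one percentage per woman and is not touched by this concern.

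**Inputs.**
- Scores after randomization in pregnancy: week 3 plus 2 to 8 monthly visits, so m = 3 to 9 (Table 3, section 8.6).
- Scores postpartum: m = 5 (Table 3).
- Women per arm: about 100 (section 6.2, 1:1 allocation).
- Two-sided 5% level: assumed, because the plan sets none for craving.
- Within-woman correlation ρ: not given; 0.1 to 0.7 assumed.

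**Reading 1: every visit is an independent row.** The variance of the arm difference is understated by the factor 1 + (m−1)ρ. The actual error rate is 2 × [1 − Φ(1.96/√(1+(m−1)ρ))]. For example, m = 5 and ρ = 0.5 give a factor of 3.0, and 1.96/1.732 = 1.132, so the rate is 25.8%.

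| m | ρ = 0.1 | 0.3 | 0.5 | 0.7 |
|---|---|---|---|---|
| 3 | 7.4% | 12.1% | 16.6% | 20.6% |
| 5 | 9.8% | 18.6% | 25.8% | 31.5% |
| 9 | 14.4% | 28.8% | 38.1% | 44.6% |

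Simulation (3,000 null trials per setting, 100 women per arm, visits uniform on 3 to 9) gave 25.2%, 31.7% and 37.6% at ρ = 0.3, 0.5 and 0.7.

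**Reading 2: one mean per woman.** The same simulations, with full attendance, gave 4.6% to 6.4%, which is nominal within simulation error.

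The remaining issue is unequal retention combined with a decline in craving shared by both arms. A woman who leaves early contributes only early, higher scores. Simulation put the resulting bias at about 0.01 to 0.05 SD, assuming a shared decline of 0.5 to 1 SD and retention of 57.7% versus 78.1%, or 38% versus 64%.

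A hand check uses five visits and a linear decline of D from first to last, with leavers equally likely to give 1 to 4 scores. A completer's mean is −D/2. A leaver with k scores has mean −D(k−1)/8, which averages −0.1875D over k = 1 to 4. The gap is 0.3125D. With a retention difference of 0.781 − 0.577 = 0.204, the bias is 0.204 × 0.3125D = 0.064D, or 0.032 SD at D = 0.5. It is proportional to D, so D = 1 gives 0.064 SD, somewhat above the simulated range. The order of magnitude is a few hundredths of an SD.

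**Value of the baseline score.** Take unit variance and the same ρ between baseline and each later score. The variance of a woman's mean is (1+(m−1)ρ)/m, and baseline adjustment subtracts ρ². At m = 5:
- ρ = 0.3: 0.44 falls to 0.35, so the standard error falls by 1 − √(0.35/0.44) = 11%.
- ρ = 0.5: 0.60 falls to 0.35, a reduction of 24%.
- ρ = 0.7: 0.76 falls to 0.27, a reduction of 40%.

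Simulation of the baseline-adjusted mixed model gave a reduction of about 13% to 40%.

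**The case against.** The strongest reply is that the plan never says visit rows will be pooled. Craving sits beside outcomes with one value per participant, so a per-woman summary is at least as natural a reading, and repeated-measures ANOVA also fits the words. The open-ended alternative leaves room for a mixed model, and the HADS model is itself only something that may be used. All of this stands.

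A reader might infer that the plan commits to a test with a false-positive rate of some 25% to 30%. The documents do not support that. It needs visit-level pooling, which is not stated, and a particular correlation: about 0.48 to 0.64 at five visits, or 0.24 to 0.32 at nine. No correlation and no significance level for craving are given. The test is also two-sided, so only about half of any false rejections would favour BUP-XR.

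The retention argument is weak as well. The 57.7% and 78.1% in section 4.1.2 are buprenorphine versus methadone. The 38% and 64% match the complements of the postpartum dropout figures there (up to 62% by 6 months and 36% by 3 months), which are two time points. Neither pair compares BUP-XR with BUP-SL, so both serve only as assumed gaps.

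A defined per-woman mean with baseline adjustment would also hold test size and gain most of the precision. What remains is that the plan defines neither that summary nor any other. The protocol mentions a standalone SAP only for the power simulation, so nothing here shows that the gap is closed elsewhere.

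**Conclusion.** The concern holds as a gap in specification. The unit of analysis for craving is undefined, and neither method named in section 10.3.3 handles within-woman correlation in its ordinary form.

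The consequence depends on which reading is used. Pooling visits would give a false-positive rate of about 7% to 45% at a nominal 5% (level assumed, correlation 0.1 to 0.7 assumed, 3 to 9 visits). Averaging per woman would keep about 5%, with a possible bias of a few hundredths of an SD toward the better-retained arm on assumed decline and retention. Without baseline adjustment it would also leave a standard error about 11% to 40% larger than need be, measured as the reduction forgone at five visits with correlation 0.3 to 0.7.

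The matter is confined to a non-key secondary outcome. It is worth correcting because the correction is cheap and removes the dependence on an unstated reading.

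**What to change.** In section 10.3.3 and the SAP, take craving out of the ANOVA list. Analyse the post-randomization scores separately for pregnancy and postpartum with a repeated-measures mixed model containing:
- arm, visit and arm-by-visit, using time since randomization in pregnancy because the number of monthly visits varies from 2 to 8;
- the baseline craving score;
- a within-woman random effect or a simple covariance structure. An unstructured matrix would be poorly supported at the later pregnancy visits.

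State the test as the between-arm contrast over a fixed set of visits common to most women. In pregnancy this could be week 3 and the first two monthly visits, which is the minimum schedule implied by section 8.6. Postpartum it could be the five scheduled visits. State the significance level. Keep ANOVA for outcomes with one value per participant.

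The cost is about one sentence and a slightly more complex model, and no data beyond what Table 3 already collects. The model relies on missing visits being explained by the observed scores, which should be stated.
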